1.2 Schedule of Assessments

Following screening, informed consent, and confirmation that a patient with severe COVID-19 meets all eligibility criteria, subjects will be randomized 1:1 to receive duvelisib 25 mg, po BID or a placebo pill, po BID. Randomization between duvelisib 25 mg po BID and placebo BID will be stratified by study site. The investigational pharmacy will supply coded study drug based upon the results of central randomization.

Procedures and Tests Study Tests DURING HOSPITALIZATION [#]	Days -2 to 0 [@]	Day 1 [@]	Day 8 (± 2)	Day 15 (± 2)	Day 29 (± 3)	Day 50-60
Randomization to duvelisib or placebo arm	X					
Study Drug Administration		Oral drug BID Days 1-14				
SARS-CoV-2 RT-PCR	X					
Immunophenotyping of immune cells in blood		X	X	X	X	
Whole blood for RNA gene expression ^{##}		X	X	X	X	
Mononuclear cells for mass cytometry ^{##}		X	X	X	X	
Plasma cytokines and chemokines ^{##}		X	X	X	X	
Anti-SARS Cov-2 IgG		X			X	
TSH	X				X	
Hepatitis Serologies if known history of treated Hepatitis B or C	X					

Standard of Care Tests*	Days -2 to 0	Day 1	Day 8 (± 2)	Day 15 (± 2)	Day 29 (± 3)	Day 50-60
Physical Exam	X	Performed daily during hospitalization				
ECOG Performance Status	X	Performed daily during hospitalization				
Vital Signs	X	Performed daily during hospitalization				
Clinical Labs: Record data in eCRF (REDCap) during hospitalization as shown below						
CBC with differential	X	Abstract data as available				
CMP	X	Abstract data as available				
Ferritin		Abstract data as available				
CRP, Troponin		Abstract data as available				
Coagulation Tests**		Abstract data as available				
Non-contrast Chest CT or Chest X-Ray	X	Abstract data as available				
Serum or Urine Pregnancy Test***	X					
Assessment of Survival Status						X

study procedures which are performed as part of the research protocol and covered by the study budget

Additional research blood samples will be obtained prior to discharge from hospital

@ Some overlap of procedures and tests performed for screening and Day 1 is expected.

* Standard of care procedures which are routinely performed on COVID-19 patients and the results of which will be recorded as part of study conduct

** PT/INR, PTT, Fibrinogen, D-Dimer, Heparin/Enoxaparin Anti Xa

*** Pregnancy test for WOCBP may be obtained after hospital admission but prior to study enrollment

2. Objectives (and Endpoints)

OBJECTIVES	ENDPOINTS
Primary	

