To compare the incidence of mechanical ventilation or death in subjects with severe COVID-19 given placebo or oral duvelisib.	The primary end-point is a composite endpoint of mechanical ventilation or death within 4 weeks of randomization.
Secondary	
Secondary Objectives are to compare the duvelisib cohort to the placebo cohort with respect to:
 
1) Days to recovery as assessed by ACTT endpoints as the time to recovery (Day 1 through Day 29) to satisfy a score of ≥ 5 from the following eight categories from the NIAID ordinal scale. The scale is as follows: 1. Death; 2. Hospitalized, on invasive mechanical ventilation or extracorporeal membrane oxygenation (ECMO); 3. Hospitalized, on non-invasive ventilation or high flow oxygen devices; 4. Hospitalized, requiring supplemental oxygen; 5. Hospitalized, not requiring supplemental oxygen - requiring ongoing medical care (COVID-19 related or otherwise); 6. Hospitalized, not requiring supplemental oxygen - no longer requires ongoing medical care; 7. Not hospitalized, limitation on activities and/or requiring home oxygen; 8. Not hospitalized, no limitations on activities.2) Duration of hospitalization3) Death within 29 days of randomization4) ICU transfer within 29 days of randomization5) ECOG performance status at day 15 and 29 of randomization6) Incidence of grade III-V adverse events or SAEs (as defined by CTCAE version 5)7) Documented secondary bacterial or viral infection within 29 days of randomization.8) Mean frequencies of Th1 and Th17 T cells in blood mononuclear cells at 1, 2 and 4 weeks9) Mean levels of inflammatory serum biomarkers at 1, 2 and 4 weeks10) Gene expression profiles of T cells at 1, 2 and 4 weeks

OBJECTIVES	ENDPOINTS
11) Median titers of IgG antibodies to SARS-CoV-2 at 4 weeks 12) Survival at day 50-60 after randomization	

3. Background

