- EKG as ordered by attending physician
- Labs: Complete Blood Count (includes hemoglobin, platelets, and white blood cell count with differential), Comprehensive metabolic panel (includes sodium, potassium, chloride, creatinine, AST, ALT, total bilirubin, and alkaline phosphatase), ferritin, D-dimer, CRP, troponin (abstract from SOC labs daily or as available), Thyroid Stimulating Hormone (TSH, Day 29)
- Immune phenotyping of leukocytes (days 1, 8, 15, and 29)
- Whole blood for RNA – gene expression analyses (days 1, 8, 15, and 29)
- Mononuclear cells for mass cytometry (CyTOF) (days 1, 8, 15, and 29)
- Plasma for cytokine/chemokine analyses (days 1, 8, 15, and 29)
- Serum for antibodies to SARS-CoV-2 (screening and 29)

Follow-up Phase:

- Survival status on day 50 - 60

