Blood samples for chemistry, hematology, viral serologies, leukocyte immunophenotyping and pregnancy (for pre-menopausal patients) will be analyzed at Emory or secondary site clinical laboratories. The chemistry panel will include sodium, potassium, chloride, bicarbonate, glucose, BUN, AST, ALT, total bilirubin, total protein, ferritin, D-dimer, CRP will be tested at screening and on days 1, 8, 15, and 29. TSH will be tested at screening and at day 29. Hematology panel includes complete blood count, including white blood cell count with differential (neutrophils, lymphocytes, eosinophils, basophils), red blood cell count, hemoglobin, hematocrit and platelet count will be tested at screening and days 1, 8, 15, and 29. Hepatitis viral serologies will be tested at screening if a patient has a prior history of treated hepatitis B or C, and include:

- Hepatitis B Panel (HBsAg, HBsAb, HBcAb and HBV DNA PCR)
- Hepatitis C Panel (HCV Ab and HCV PCR)

Correlative Laboratory Data

- SARS-CoV-2 RT-PCR test from nasopharyngeal swabs will be ordered at screening [baseline, prior to study drug]. Results are returned as positive or negative, with Ct values for positive tests. Note: saliva SARS-CoV-2 PCR test will be added once available.
- Leukocyte immunophenotyping (via flow cytometry/fluorescence-activated cell sorting) will be done at days 1, 8, 15, and 29. This will determine the amount of B/T/NK cells and more specifically, the phenotypes and frequencies of these immune cell populations pre and post duvelisib exposure (Th1 and Th17 T cells).
- Mononuclear cells collected at days 1, 8, 15, and 29 will be stored for CyTOF analyses for more in-depth immune-phenotyping in follow-up studies.
- Blood cells collected at days 1, 8, 15, and 29 will also be collected in RNA stabilization tubes for immunological gene expression analyses.

Protocol Title: Duvelisib Ameliorates Manifestations of Pneumonia in Established Novel Coronavirus Infection (DAMPEN-CI)

- Mean levels of inflammatory serum biomarkers will be measured by ELISA at day 1 [baseline, prior to study drug], during and following 2 weeks of study drug exposure in each cohort, using samples at days 1, 8, 15, and 29
- Median titers of neutralizing antibodies to SARS-CoV-2 will be determined at days 1 and 29.

6. Data and Specimen Banking

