Immune related toxicities are the most common non-hematological adverse event (AE) with duvelisib. Elevated AST/ALT and diarrhea are the most common non-hematological AEs. The rates of diarrhea ranged from 42-51% in clinical trials with a median onset of 2.2-4 months (28, 8). The median time of onset for AST/ALT elevation was 1.2 months and occurred in 39% of patients in one phase I clinical trial (28). Other non-hematological AE's that have been reported include:

- 1) risk of infection (reported in 61-69% of patients with upper respiratory tract infections and pneumonia being the most common infections (8, 29).) There have also been reports of *Pneumocystis jirovecii* with the use of duvelisib.
- 2) risk of pneumonitis,
- 3) risk of intestinal infection and colitis,
- 4) risk of severe skin reactions (maculopapular rash)
- 5) Neutropenia (the most common hematological AE, occurring in 29%-39% of patients in clinical trials)
- 6) pyrexia

Other Risks:

Risk of Phlebotomy- The primary risks of phlebotomy include local discomfort, occasional bleeding or bruising of the skin at the site of needle puncture, and rarely hematoma, infection, or fainting. At the time of enrollment and during study visits, each participant will be asked about participation in other research studies to ensure that blood draws do not exceed the following amounts for all research protocols combined: 10.5 mL/kg or 550 mL, whichever is smaller, over any 8-week period for adults, and no more than 5 mL/kg may in a single day (no more than 9.5 mL/kg may be drawn over any 8-week period) for persons under the age of 18.

Risk of Nasopharyngeal Swab- The primary risk of a nasal swab is local discomfort. Rarely, there can be local bleeding from the nasal mucosa, which is controlled with local measures such as pressure or packing with gauze.

Risk of Oropharyngeal Swab- The primary risk of an oropharyngeal swab is local discomfort. This swab can stimulate the gag reflex, and very rarely vomiting.

Risk of Endotracheal Aspirate- The primary risk of endotracheal aspirate is cough, and rarely can cause a small amount of bleeding.

Data security- Subjects will be asked to provide personal health information (PHI). All attempts will be made to keep this PHI confidential within the limits of the law. However, there is a chance that unauthorized persons will

Protocol Title: Duvelisib Ameliorates Manifestations of Pneumonia in Established Novel Coronavirus Infection (DAMPEN-CI)

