Evaluable subjects will be all subjects who were randomized to receive duvelisib or placebo. The definition of secondary endpoints are listed in section 2. The descriptive statistics will mainly be applied to all secondary endpoints by treatment arms separately, such as frequency and percentage for categorical endpoints and mean, median, and standard deviation for numerical endpoints. They will be compared between treatment arms by Fisher's Exact test for categorical endpoints and Wilcoxon Rank-Sum test for numerical endpoints. For biomarkers measured repeated over time, generalized estimating equation (GEE) model will be used to test the difference in change pattern over time by two treatment groups using a nonlinear model. P-value will be adjusted for multiple comparison if necessary. Time to recovery is as the days from randomization to reach the desired NIAID ordinal scale ≥ 5 , a log-rank test will be used to compare the difference between the two arms. Survival rate at day 50 - 60 will be estimated by Kaplan-Meier method with log-rank test.

Interim Analysis for futility

The responsibility of any data-informed recommendations regarding continuing/stopping the study or modifying the study design/protocol be restricted to the independent data monitoring committee (IDMC), which is a part of the Winship data safety monitoring committee (DSMC). Upon 20 enrolled for each arm, an interim analysis will be carried out by two-sided Mantel-Haenszel test. O'Brien-Fleming boundary for futility is 2.373 on the Z score (equivalently: 0.991 on the fixed sample p-value scale). The trial may be terminated due to futility, or

Protocol Title: Duvelisib Ameliorates Manifestations of Pneumonia in Established Novel Coronavirus Infection (DAMPEN-CI)

following review by the IDMC of clinical and laboratory immune-monitoring data. Otherwise, the trial will continue enrolling patients until all 80 patients enrolled.

Stopping Rule for Safety

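### The secondary endpoint is gene expression of T cells, but the only RNA specimen is whole blood, so a change in blood-cell mix could be reported as, or could hide, a T-cell effect

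*Combined protocol and SAP*

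**What the plan says.** The endpoint appears three times with the same content: under Objectives and under Endpoints in the synopsis (section 1.1), and in section 2: "Gene expression profiles of T cells at 1, 2 and 4 weeks".

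The specimen is described in three other places:

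- Schedule of Assessments (section 1.2): "Whole blood for RNA gene expression", on days 1, 8, 15 and 29.
- Treatment-phase list in section 5.5: again whole blood for RNA, on the same four days.
- Correlative Laboratory Data in section 5.6: "Blood cells collected at days 1, 8, 15, and 29 will also be collected in RNA stabilization tubes for immunological gene expression analyses".

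Two other cell specimens are drawn on those days, each with its own use. Of the mononuclear cells, section 5.6 says: "Mononuclear cells collected at days 1, 8, 15, and 29 will be stored for CyTOF analyses for more in-depth immune-phenotyping in follow-up studies". Of flow cytometry, it says: "This will determine the amount of B/T/NK cells and more specifically, the phenotypes and frequencies of these immune cell populations". Appendix G, on the analysis of T cells, covers freezing, thawing, dilution, plating or culture, and shipment.

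Section 15.1 has no analysis specific to gene expression. For biomarkers measured repeatedly, a "generalized estimating equation (GEE) model will be used to test the difference in change pattern over time by two treatment groups".

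**The concern.** The trial's mechanistic hypothesis concerns what happens inside T cells. Sections 3.4 and 3.5 speak of exhaustion and of lower PD-1, TIM-3 and LAG-3. RNA from whole blood sums over all leukocytes, so the measured level of a T-cell gene depends both on expression per T cell and on the share of T cells in the sample. Only the first is a T-cell expression profile.

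Randomization balances the cell mix at baseline in expectation. It does not balance a change in mix that the drug itself causes. The documents give some reason to allow for one: section 13 lists neutropenia in 29% to 39% of patients in earlier duvelisib trials, section 15.1 makes neutropenia a primary safety endpoint, and section 3.5 reports a doubling of net T-cell expansion in culture. If the mix differs between arms after treatment, a statement that duvelisib altered T-cell gene expression would not follow from the data. Nor would a statement that it did not.

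**Working it through.** **1. Is there a planned route from specimen to endpoint?** The plan states no figure to reproduce here, so the first check is textual.

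| Specimen (days 1, 8, 15, 29) | Assigned use | Gives T-cell RNA as written? |
|---|---|---|
| Whole blood in RNA stabilization tubes (1.2, 5.5, 5.6) | Gene expression | No; no separation step is described |
| Mononuclear cells (1.2, 5.6) | Storage for mass cytometry in follow-up studies | No; not assigned to RNA |
| Leukocytes for flow cytometry (5.6) | Amounts, phenotypes and frequencies | No; no RNA step |
| Cryopreserved cells (Appendix G) | Freeze, thaw, culture or use, ship | No; no T-cell separation or RNA extraction |

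Section 15.1 names no deconvolution and no composition term. No route is planned.

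**2. How far can cell mix alone move the signal?** All counts in this step are assumptions; the documents give none. RNA per cell is taken as equal across cell types.

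Let f be the T-cell share of leukocytes, T the expression per T cell (held at 1 throughout), and O the expression in other cells. The bulk signal is B = f × T + (1 − f) × O.

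Assume per mcL: neutrophils 5,000; lymphocytes 700, of which 70% = 490 are T cells; other leukocytes 300. Let neutrophils fall to 2,000 and nothing else change.

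- Before: f = 490 / (5,000 + 700 + 300) = 490 / 6,000 = 8.2%.
- After: f = 490 / (2,000 + 700 + 300) = 490 / 3,000 = 16.3%.
- O = 0 (gene absent from all other cells): 16.3 / 8.2 = 2.0-fold, log2 = 1.0.
- O = 0.1: before 0.0817 + 0.9183 × 0.1 = 0.1735; after 0.1633 + 0.8367 × 0.1 = 0.2470; ratio 1.42-fold, log2 about 0.51.

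Other assumed counts, with T cells and neutrophils as the only cells:

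| Change per mm³ | f before → after | Fold, O = 0 | Fold, O = 0.1 |
|---|---|---|---|
| T 500; neutrophils 6,000 → 3,000 | 7.7% → 14.3% | 1.86 | 1.35 |
| T 500; neutrophils 4,000 → 2,000 | 11.1% → 20.0% | 1.80 | 1.40 |
| T 500; neutrophils 6,000 → 1,000 | 7.7% → 33.3% | 4.33 | 2.36 |
| Neutrophils 6,000; T 500 → 1,000 | 7.7% → 14.3% | 1.86 | 1.35 |

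Apart from the extreme fall to 1,000, the range is about 1.4- to 2-fold for one patient. The same shift can hide an effect: if expression per T cell were halved and composition doubled the signal, the result would be 0.5 × 2 = 1, no visible change.

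**3. What would that be as an arm mean?** Suppose only patients with neutropenia have the fall in step 2 (log2 = 1.0), and take 29% to 39% on duvelisib from section 13.

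- No such fall on placebo: mean log2 shift 0.29 to 0.39.
- Net of the 24% placebo neutropenia rate assumed in section 15.1: 0.29 − 0.24 = 0.05, to 0.39 − 0.24 = 0.15.

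These are illustrations; the definition of neutropenia may differ between the two sections. They show that the arm-level shift is well below the single-patient figure.

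**The case against.** A reader might infer that the endpoint cannot be derived at all. The documents do not support that. Mononuclear cells are collected on the same four days, cell sorting is named among the flow methods, and Appendix G ends with thawed cells cultured or used at once. T-cell RNA is therefore unplanned, not impossible.

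A reader might also take the 2-fold figure as the expected difference between arms. That is not supported either. It is one patient, on assumed counts, for a transcript absent from every other leukocyte.

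The evidence for a drug-induced shift in mix is indirect:

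- The T-cell expansion and the higher CD8 frequency come mostly from culture (sections 3.1 and 3.5), and a CD8 shift does not by itself change the T-cell share of leukocytes.
- The neutropenia figure comes from earlier duvelisib trials; the approved uses and phase 1 experience that the protocol describes are in hematological malignancy. Dosing here lasts at most 14 days.
- Section 3.6 says the class can be given for weeks to months without significant hematological toxicity.
- Only the excess over placebo can bias a randomized comparison.

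Finally, this is one item in a long list of secondary endpoints that are handled mainly by description, and Th1 and Th17 frequencies by flow are a separate, T-cell-specific endpoint.

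All of this stands, and it limits the size and reach of the problem. It does not remove the mismatch between the named endpoint and the named specimen, which depends on none of the assumed counts.

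**Conclusion.** The point holds as a mismatch between endpoint and specimen. The plan as written would deliver a whole-blood expression result under a T-cell label, with nothing planned to separate expression per cell from cell mix. That the sample is unsorted is inferred from its description as whole blood and from the absence of any separation step.

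The size of any resulting error is unknown. It rests on assumed counts, on equal RNA per cell, and on how far other leukocytes express the gene. About 1.4- to 2-fold is a fair illustration for a single patient with a large neutrophil fall; an arm mean would be smaller. The consequence is confined to the interpretation of one correlative secondary endpoint. It should be corrected because it determines what that endpoint can be said to show and because the correction is cheap.

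**What to change.** 1. In the synopsis (Objectives and Endpoints) and in section 2, rename the endpoint as whole-blood gene expression profiles at 1, 2 and 4 weeks, and limit the conclusion to that.
2. In section 15.1, keep the unadjusted comparison between arms as the main result. Prespecify a sensitivity analysis adjusted for same-day leukocyte composition: B, T and NK cells from the flow panel, and the blood-count differential where available.
3. State beside it that composition is measured after randomization and may lie on the causal path. The adjusted result can therefore remove part of a genuine effect that acts through cell numbers. It is read next to the unadjusted result and does not replace it.
4. Report how many patients have both RNA and composition at each visit. Section 1.2 takes the blood count only as available, and section 8.1 follows discharged patients by telephone at days 15 and 29, with a blood draw only after day 29 where possible.

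The cost is a wording change in three places and a short paragraph in section 15.1, using data already planned; the mechanistic claim becomes narrower. Separating T cells for RNA would allow the T-cell wording to stay, but it is optional and not part of this low-cost change: it adds laboratory work and uses stored cells already assigned to mass cytometry.

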8.1 Duration of therapy and follow up

In the absence of treatment delays due to adverse event(s), subjects will be treated for 14 days with duvelisib/placebo. A subject will be considered to have completed the study if he or she has completed all phases of the study including the last visit or the last scheduled procedure shown in the schedule of activities. Subjects who have signed consent, are deemed eligible and are randomized to receive study drug (duvelisib/placebo) will be considered evaluable for efficacy endpoints on an intent-to-treat basis. Subjects who receive at least one dose of study drug (duvelisib/placebo) will be evaluable for toxicity. The end of the study is defined as completion of the last visit or procedure in SOA (Day 29) and an assessment of survival status on day 50 - 60. In the event of a subject's withdrawal, the Investigator will make every effort to complete the End of Treatment procedures specified in the Schedule of Events. Subjects who withdraw from the study will be encouraged to permit follow-up for clinical end-points, including death, mechanical ventilation (e.g. intubation, high-flow O₂ Bi-PAP or AIRVO), hospital discharge, and need for supplemental oxygenation. Subjects will be assessed daily while hospitalized. If the subjects are discharged from the hospital, they will have phone follow-up calls with a study team member at

Protocol Title: Duvelisib Ameliorates Manifestations of Pneumonia in Established Novel Coronavirus Infection (DAMPEN-CI)

day 15 (window d13 – 25), and at day 29 (window d27 - 39) for clinical outcomes data. Arrangements will be made for an outpatient phlebotomy appointment after day 29 (day 30 - day 60 if possible, but up to day 100) to obtain safety laboratory tests and blood samples for secondary research. Patients will receive \$100 compensation for the in-person follow-up phlebotomy visit. However, travel distance, infection control or other restrictions may limit the ability of the subject to return to the clinic. In such cases, only clinical data will be obtained via the d27 - 39 call.

Patients removed from study for unacceptable adverse event(s) will be followed until resolution or stabilization of the adverse event and for key clinical end-points including death, mechanical ventilation (e.g. intubation, high-flow O₂ Bi-PAP or AIRVO), hospital discharge, and need for supplemental oxygenation. Survival status of each subject will be assessed by reference to documentation in EMR of non-protocol specified in-person or tele-medicine visits that occurred on or following day 50 - 60, contacting the patient by phone or text, contacting known associate of the patient, or through a search of vital records.

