At the interim analysis (20 patients/arm), the incidence of death or mechanical ventilation, grade ≥ 3 elevations in liver transaminases, or neutropenia will be estimated. We assume that the underline rate is 40%, 10%, or 24% for the three incidences in placebo group respectively, and if the rate in duvelisib group is $\geq 15\%$ higher than that in the placebo group in either of the three incidences, the trial may be stopped due to the safety concern. It also translates to stop the study if 3 or more excess events in duvelisib group are observed in either of the three incidences. Operating Characteristics, the probability of trial stopping due to ≥ 3 excess events based one simulation study, is listed in the below table.

AEs	Underline event rate in Placebo arm	Underline event rate in Duvelisib arm						
		5%	10%	20%	30%	40%	50%	60%
death or mechanical ventilation	40%	0%	0.02%	0.7%	4.8%	16.6%	37.4%	62.7%
grade ≥ 3 elevations in liver transaminases	10%	0.79%	5.7%	32.8%	65.8%	87.9%	97.2%	99.7%
neutropenia	24%	0.07%	0.6%	7.3%	26.1%	52.7%	77.3%	92.6%

In addition to the study stopping rules based an interim analysis, the Independent Data Monitoring Committee (IDMC) will review, on a monthly basis, the number of Grade 3 and/or Grade 4 adverse events in each arm, including neutropenia and elevated transaminases, and consider stopping or suspending accrual to the study if the frequencies of Grade 3 or Grade 4 adverse events are significantly higher among subjects in the duvelisib arm compared with subjects in the control arm.

Analysis of Safety Data

The primary safety endpoints include death or mechanical ventilation, grade ≥ 3 elvation in liver transminases, and neutropenia within 4 weeks. The cumulative incidence rate of each safety endpoint will be calculated with 95% confidence interval by randomized arms, and compared by Fisher's exact test.

Handing of Missing Data

For the safety endpoints and secondary endpoints, missing data will not be imputed, summaries and analyses will be based on the observed cases. For the primary efficacy analysis, every effort will be made from the informed consent form design to clinical follow up to reduce the missing data. Patients withdraw consent before the primary endpoint can be measured will be replaced.

Demographics and Baseline Characteristics

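### After discharge the plan provides no week-1 or week-2 research blood and at most one late draw, so observed-case biomarker and antibody comparisons depend on who recovers and when

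*Combined protocol and SAP*

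**What the plan says.** The Section 2 objectives compare the arms on Th1/Th17 frequencies, T-cell gene expression and "Mean levels of inflammatory serum biomarkers at 1, 2 and 4 weeks", and on "Median titers of IgG antibodies to SARS-CoV-2 at 4 weeks". Section 5.6 ties the repeated markers to days 1, 8, 15 and 29.

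In the Schedule of Assessments the research draws sit under the header "Procedures and Tests Study Tests DURING HOSPITALIZATION", with windows Day 8 ± 2, Day 15 ± 2 and Day 29 ± 3. A footnote adds: "Additional research blood samples will be obtained prior to discharge from hospital". Its marker is missing from the text I have. It appears to belong to the rows for RNA, mass cytometry and plasma cytokines, and not to the immunophenotyping or IgG rows.

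For discharged patients, Section 8.1 says "they will have phone follow-up calls with a study team member at" day 15 (days 13-25) and day 29 (days 27-39), to collect clinical outcomes. It then arranges one "outpatient phlebotomy appointment after day 29 (day 30 - day 60 if possible, but up to day 100"), for safety tests and secondary research samples. If the patient cannot return, "only clinical data will be obtained via the d27 - 39 call". Section 15.2, on capturing the primary endpoint, mentions in-person or telehealth follow-up of patients discharged before day 29 but no blood draw.

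Section 15.1 compares numerical secondary endpoints by Wilcoxon test and repeated biomarkers by a GEE model, for which it states no weighting and no term for actual sampling day. For safety and secondary endpoints, "missing data will not be imputed, summaries and analyses will be based on the observed cases".

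**The concern.** Discharge follows recovery, and recovery is what the drug is meant to bring forward. If blood comes mainly from patients still in hospital, the week-1 and week-2 comparisons are made among patients selected after randomization, possibly to a different degree in each arm. At week 4, patients still in hospital can be sampled near day 29. Recovered patients are sampled later or not at all, while inflammatory markers and antibody titres may still be changing. An observed-case comparison, or a GEE without weighting, is generally valid only if absence is unrelated to the marker, which is hard to accept for inflammation in this population.

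The synopsis lists inflammatory biomarkers and the IgG response among the key secondary endpoints. Section 15.1 also lets the monitoring committee's review of laboratory immune-monitoring data contribute to a decision to terminate. A distorted marker comparison could therefore affect decisions about the drug.

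**Working it through.** **No plan figure to reproduce.** The documents give no length of stay, no expected sample numbers and no power for any biomarker.

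**Timing, from the stated windows.**
- Week 1: 8 ± 2 = days 6-10. Week 2: 15 ± 2 = days 13-17. Week 4: 29 ± 3 = days 26-32.
- Post-discharge draw: days 30-100, which is 100 - 30 + 1 = 71 days. Days 30, 31 and 32 fall inside the week-4 window, so 3 of 71.
- Distance from day 29: 30 - 29 = 1 day to 100 - 29 = 71 days, or up to 60 - 29 = 31 days if the preferred period is met.
- The pre-discharge sample supplies an in-window week-1 value only if discharge falls on days 6-10, and an in-window week-2 value only on days 13-17. A patient discharged before day 6 has neither.

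**Size of the selection effect, on assumed inputs.** Let discharge severity be N(0,1) on placebo and shifted by -0.50 SD on duvelisib. Patients below a common threshold c have gone home. Half of placebo patients are home, so c = 0. The marker has SD 1, true drug effect Δ, and correlation r with severity within each arm.

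Still in hospital: placebo 1 - Φ(0) = 50%; duvelisib 1 - Φ(0.5) = 31%.

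Mean severity of those remaining, measured from their own arm's mean:
- placebo: φ(0)/[1 - Φ(0)] = 0.798
- duvelisib: φ(0.5)/[1 - Φ(0.5)] = 1.141

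Observed marker difference = Δ + r × (1.141 - 0.798) = Δ + 0.343r.

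With Δ = -0.50:

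| r | Observed difference (SD) | Attenuation = 0.343r/0.50 |
|---|---|---|
| 0.3 | -0.397 | 21% |
| 0.5 | -0.328 | 34% |
| 0.7 | -0.260 | 48% |
| 1 | -0.157 | 69% |

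With Δ = 0 (the drug speeds discharge but leaves the marker alone), the same formula gives a spurious +0.10 SD at r = 0.3 and +0.24 SD at r = 0.7, so duvelisib looks more inflamed. A simulation with no marker effect, 30-60% of placebo and 15-40% of duvelisib patients still in hospital, and r from 0.3 to 0.7 gave +0.09 to +0.28 SD. With equal in-hospital fractions (60% in each arm) it gave 0.

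**The case against.** Several points on the other side carry weight.

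- **The pre-discharge sample.** A reader might infer that anyone discharged in the first week has no week-1 value. The documents do not support that: discharge on day 6 lies inside the Day 8 window, and the pre-discharge draw then supplies an in-window value, at least for the rows the footnote appears to cover. What stands is that the sample's day is set by discharge, no analysis rule uses it, and it may not extend to Th1/Th17 or IgG.
- **No sentence forbids an outpatient draw at day 8 or 15.** In-hospital sampling is read from the schedule header together with the call-based follow-up in Section 8.1. Section 15.2 allows in-person visits. But no section arranges blood at those times after discharge.
- **The late draw is never labelled the 4-week sample.** Treating it as such is an inference. If it is not that sample, a patient discharged before the Day 29 window has no planned week-4 sample at all.
- **The illustration is cross-sectional and ignores the Day 1 value.** It describes the visit-wise comparisons better than the GEE on change over time, where baseline may absorb part of the selection.
- **Practical limits.** Section 8.1 openly cites travel and infection control, and Section 15.1 says the secondary analyses are mainly descriptive. Both are fair, and they argue for a change in analysis rather than more visits.

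**Conclusion.** The concern holds as a gap in the analysis plan. Followed as written, the plan compares arms at weeks 1 and 2 on samples whose presence depends on recovery. At week 4, recovery also decides whether a discharged patient is sampled and when. Day 1 samples and the primary endpoint are unaffected.

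The size of the bias is unknown, because it depends on how discharge differs by arm and how closely each marker tracks severity. On the assumed inputs above, attenuation is 21% to 48% for correlations of 0.3 to 0.7.

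Two stronger readings should not be drawn:
- **That well over half of a real effect would be lost.** The 69% figure requires the marker to determine discharge completely (r = 1).
- **That a real benefit of this size would reverse.** In the worked case it cannot. Even at r = 1 the duvelisib patients still in hospital average -0.50 + 1.141 = 0.641, against 0.798 on placebo, so they remain less inflamed. A change of sign needs a true marker effect smaller than 0.343r, for instance below about 0.17 SD at r = 0.5, alongside a drug effect on discharge. If in-hospital fractions and selection are equal, there is no bias.

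**What to change.** 1. For the repeated biomarkers, replace the observed-case visit comparisons and the GEE with a likelihood-based mixed model. Include actual study day, the Day 1 value and every sample, including the pre-discharge one. State that the model assumes missingness is explained by observed values, and that results are interpreted for patients while alive.
2. Count a draw as 4 weeks only within Day 29 ± 3 (days 26-32), or within one stated wider window applied to both arms. Report later draws separately by actual day, including for IgG.
3. Report the number of samples, and the reasons for absence (discharge, death, non-return), by arm and visit.
4. Reconcile the Schedule of Assessments and Sections 5.6, 8.1 and 15.2 on what blood is drawn after discharge. State which assays the pre-discharge sample covers and whether the late draw serves the 4-week objectives.

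The cost is analysis-plan wording and some extra modelling, with no new visits or samples. Fewer draws will count as 4 weeks. The model's missing-data assumption is untestable, though weaker than what the present plan needs.
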